4.4 Inclusion\Exclusion Criteria

4.4.1 Inclusion Criteria

Because this is a site-wide intervention, all patients who have a COPD exacerbation, as determined by their clinical care provider will be subject to receiving components of the intervention. Patients will be included in the daily Gap List based on the following criteria:

- ≥ 40 years of age at time of admission
- Identified as having an acute exacerbation of COPD within 24 hours of admission

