5.1.2 Secondary Outcome Variable(s)

Secondary outcome variables of the evaluation include:

Examining the COPD clinical pathway's effect on additional patient outcomes, such as the

- i. CHS Quality, Comfort, and Care 30-day readmission rate. This is a readmission rate among patients with an inpatient readmission to the same CHS facility as the index encounter.
- j. The patient-centric 30-day readmission rate. This is a readmission rate among patients with an inpatient or observation readmission to any CHS facility.
- k. The patient-centric 30-day readmission rate where the primary diagnosis of the readmission is COPD.
- l. Length of stay
- m. Rate of follow-up visit within 5 days of discharge.
- n. Antibiotic order rate during admission
- o. Steroid order rate during admission
- p. Short acting bronchodilator order rate during admission

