5.2.5 Primary aim

The primary outcome for this study is 60-day non-elective acute care utilization. Characteristics of the hospitals and individuals will be summarized by levels of randomization steps, hospitals and individuals. The count, rates and 95% confidence intervals of 60-day non-elective acute care utilization in the -control period will be presented and compared with that in the -treatment period. The primary analysis will be conducted using generalized estimating equations with fixed effects for intervention, time (steps), and intervention multiply by the time, accounting for the cluster randomized trial design with a random cluster (hospitals) effect. We will estimate and report the intra class correlation coefficients for all outcome measures to assess assumptions for sample size analyses and for future investigations using similar designs and outcomes. The primary analyses will follow the intention to treat principle with an additional per protocol analysis including by using denominator in those who had pathway ordered as well as intervention periods when truly occurred. The secondary analyses will include within cluster comparisons of intervention and control periods (not adjusting for any confounding effect of time), as well as comparisons of a series of (unbalanced) quasi-parallel cluster trials between those enrolled and unenrolled clusters at each intervention enrollment period. The same analyses plan will also be applied to secondary outcomes.

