7.1.4. Patient Identification and Care Gaps

Patients are identified as described in the ‘Subjects’ section. Care gaps that are monitored daily include the initiation of the COPD PowerPlan and the Respiratory therapy department COPD bronchodilator protocol. The PowerPlan includes order sets for a bronchodilator, an antibiotic, and a steroid.

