Appendix A: CHS COPD Clinical Pathway

[figure not shown]
CMC MERCY COPD PATHWAY PROGRAM – PILOT VERSION 1

Discharge Criteria | Discharge Needs | Fulfillment Options

CMC MERCY COPD PATHWAY PROGRAM – PILOT VERSION 1

Respiratory Therapy COPD Protocol

CMC MERCY COPD PATHWAY PROGRAM – PILOT VERSION 1

Respiratory Therapy COPD Assessment & Scoring

| *Bronchodilator Therapy Assessment Score | | | | | |
|---|---|--|---|--|---|
| Breath Sounds | 0 Normal/Clear | 1 End Exp. Wheeze | 2 Pronounced Exp Wheeze | 3 Insp. And Exp. Wheeze | 4 Absent or near Absent |
| Dyspnea | 0 None | 1 Slight | 2 Mid | 3 Moderate | 4 Severe |
| Total Score | 0 | 1-2 | 3-4 | 5-6 | 7-8 |
| Frequency | SABA Q4 hrs PRN for increased SOB, continue LABA and LAMA or SAMA | SABA Q4 hrs PRN for increased SOB; start or continue LABA and LAMA or SAMA | SABA and Anticholinergic Q4hrs and SABA Q2 PRN; start or continue LABA and LAMA or SAMA | SABA Q2 hrs; if on continuous then wean SABA by 5 mg/hr as tolerated down to 5 mg/hr | SABA Q1hr up to 3 treatments then start Continuous SABA and anticholinergic |
| Use SABA Albuterol 2.5mg and anticholinergic Ipratropium 0.5mg. If Xopenex ordered, follow protocol with substitution of Xopenex 0.63mg at Q8 hr frequency. | | | | | |
| If continuous therapy is indicated, then use: SABA Albuterol 15 mg/hr and Ipratropium 0.5 mg/hr, wean dose as indicated above. | | | | | |

Definitions:
LABA- long acting beta agonists
LAMA- long acting muscarinic antagonists
SABA- short acting beta agonists
SAMA- short acting muscarinic antagonists

**Nebulized steroids may be started at the discretion of the physician when long acting bronchodilators are started. The formulary recommendation is budesonide 0.5mg Q12hr. Alternatives may be prescribed at physician discretion.

Discharge Criteria
Discharge Building Blocks
Phase 1
Phase 3
RT Protocol
RT Workflow
Navigator Work Flow
Patient Education
Chart Spot Check

Phase 2
Phase 4
BTAS Table
RT Handoffs
Touchbase
Education Checklist
Transition Clinic

CMC MERCY COPD PATHWAY PROGRAM – PILOT VERSION 1

Respiratory Therapist Workflow

COPD Patient Chart Review

1. Do a chart review and check for admitting diagnosis (confirm AECOPD diagnosis, other pulmonary diagnosis or non-respiratory diagnosis)
2. Check current respiratory care medication regime including if any PRNs have been given within last 24 hours
3. Check steroid dose and modality (IV or PO)
4. Review most recent BTAS score and in-check dial completion and score.

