4. Past medical history including smoking history
5. Attending Physician

ED to Floor

1. Time of initial order
2. Time of initial treatment and any additional therapies ordered
3. BTAS score, ABG results, chest xray result and SpO2 saturation
4. Admitting Physician
5. Past medical history including smoking history

Shift to Shift

1. Time of last treatment
2. BTAS score and last in-check dial
3. Current therapies ordered
4. Past medical history including smoking history
5. Attending Physician

Discharge Criteria

Discharge Building Blocks

Phase 1

Phase 3

RT Protocol

RT Workflow

Navigator Work Flow

Patient Education

Chart Spot Check

Phase 2

Phase 4

BTAS Table

RT Handoffs

Touchbase

Education Checklist

Transition Clinic

CMC MERCY COPD PATHWAY PROGRAM – PILOT VERSION 1

COPD Pathway Coordinator Workflow

Phase 1 – Initial Patient Review & Gap Closure

1. Identify new COPD Pathway patients ([name]'s report)
2. Review EMR for COPD Pathway gaps
 - o Patient
 - o Room #
 - o PT name
 - o MRN
 - o Provider
 - o Last SABA given: where/when
 - o Home respiratory medications
3. PULMO/COPD Exacerbation PP (used)
 - o PP initiated by date-time
 - o PP RT orders modified/deselected
 - o Page Provider for Navigator call back
 - o Understand why PP was modified/deselected
 - o Could gap be closed?
4. PULMO/COPD Exacerbation (PP not used)
 - o Page Provider for Navigator call back
 - o Propose starting COPD pathway
 - o Provider to order "Initiate COPD Respiratory Protocol"
5. Notify assigned RT (Patient name, room number, MRN)
 - o Verify steroid/antibiotic ordered and administered
 - o Respiratory Therapy
 - o Initial assessment - Completed by date-time
 - o 1st inpatient SABA treatment - date/time
 - o COPD Protocol adherence
 - o Incorrect - contact assigned RT
 - o Barriers affecting accuracy
 - o Assigned RT to correct orders

Phase 2 – Plan of Care & Patient Education

1. Obtain additional EMR information
 - o Patient
 - o PCP
 - o Pulmonologist
 - o PFTs completed within last 12 months
 - o COPD Protocol
2. Respiratory Therapy adherence
3. **Patient education**
 - o Patient identified goals (Living with COPD pg. 1)
 - o General disease knowledge (Living with COPD pg. 4)
 - o Home medications (Living with COPD pg. 3)
 - o Respiratory - technique, what to use and when, side effects, tips
 - o Other - corticosteroids and antibiotics
 - o Evaluate respiratory medication self-administration (Living with COPD pg. 9,11)

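### The ordered-only per-protocol analysis makes up to three order-rate outcomes near-circular and can bias 60-day utilization either way; the ITT primary analysis is unaffected

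*Combined protocol and SAP*

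**What the plan says.** Section 5.2.5 makes intention to treat the primary approach and then adds "an additional per protocol analysis including by using denominator in those who had pathway ordered as well as intervention periods when truly occurred". This joins two different restrictions: one on patients (the pathway was ordered) and one on calendar time (the intervention period as it actually ran). The section closes its plan with "The same analyses plan will also be applied to secondary outcomes".

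Section 5.1.2 lists eight secondary outcomes. One is "Antibiotic order rate during admission"; the steroid and short-acting bronchodilator order rates are defined in the same way. Section 7.1.4 states: "The PowerPlan includes order sets for a bronchodilator, an antibiotic, and a steroid".

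The ordering event is not named. Sections 5.6 and 7.1.4 treat use of the PowerPlan and use of the respiratory therapy bronchodilator protocol as separate items. No matching restriction is stated for control patients. Section 5.2.4 allows sensitivity adjustment for baseline differences between periods, but nothing in the plan addresses selection on ordering.

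**The concern.** Hospitals are randomized to a crossover date (sections 5.2.1 and 5.2.2). Whether the order set is used is a provider's decision after admission (synopsis, Study Procedures). An ordered-only denominator therefore selects patients inside randomized hospital-periods. It can also drop patients whom the pathway reached in part, since section 4.4.1 says that "all patients who have a COPD exacerbation, as determined by their clinical care provider will be subject to receiving components of the intervention".

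Two things are at stake.

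- **Order rates.** The selection criterion contains the outcome. A high rate among ordered patients says little about whether the pathway changed prescribing.
- **60-day utilization.** If providers order the pathway for patients at lower or higher risk than the rest, the contrast mixes the pathway's effect with the choice of patients.

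Section 10 commits to a final report of all primary, secondary and exploratory findings, and section 3 says the evaluation is meant to guide system strategy. A misleading ordered-only result could be taken for the pathway's effect.

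**Working it through.** **The plan's own figures.** The plan gives no number for this analysis. Section 5.2.3 gives 43% utilization under control and 33% under intervention, a difference of 10 points and an odds ratio of (0.33/0.67)/(0.43/0.57) = 0.65. The share of patients ordered and the risk gap between ordered and other patients are not given, so both are assumed below.

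**Order rates.** Let r be the true order rate for a drug class, the same in both periods; d the rate among ordered patients; s the share ordered. With all control patients as comparator the false gain is d - r. Assume r = 80% or 90% and d = 95% or 100%.

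- r = 80%: 95 - 80 = 15 points, or 100 - 80 = 20 points.
- r = 90%: 95 - 90 = 5 points, or 100 - 90 = 10 points.

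The rate among patients not ordered is then (r - s·d)/(1 - s), which cannot be negative. So under unchanged prescribing the false gain is at most d(1 - s): with d = 100%, 20 points at s = 80% and 10 points at s = 90%. The 20-point case at s = 80% needs a rate of (80 - 80)/0.2 = 0% among those not ordered, which is arithmetically possible but clinically extreme. If controls are also restricted to ordered patients, both rates approach 100% and a real change in prescribing would be hidden.

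**Utilization, all control patients as comparator, no true effect.** Let x be the rate in ordered patients and q the rate in the others, with odds(q) = OR × odds(x) and s·x + (1 - s)·q = 0.43. Solve for x; the false contrast is 43% - x.

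Example: s = 0.6, OR = 2.0 gives x = 0.362 and q = 0.532. Check: 0.6 × 0.362 + 0.4 × 0.532 = 0.430. The false benefit is 43.0 - 36.2 = 6.8 points.

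Results in percentage points, for odds gaps of 1.25 / 1.5 / 2.0:

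| Share ordered | Lower-risk patients ordered: false benefit | Higher-risk patients ordered: false harm |
|---|---|---|
| 60% | 2.2 / 4.0 / 6.8 | 2.2 / 3.9 / 6.7 |
| 80% | 1.1 / 2.0 / 3.4 | 1.1 / 1.9 / 3.2 |
| 90% | 0.6 / 1.0 / 1.7 | 0.5 / 1.0 / 1.6 |
| 95% | 0.3 / 0.5 / 0.9 | 0.3 / 0.5 / 0.8 |

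**Utilization, controls also limited to ordered patients.** PowerPlan and respiratory protocol use are identification criteria at all eight hospitals throughout the project (sections 4.1 and 4.2), and section 9 says the care elements already exist in some facilities. Orders can therefore occur in control periods. Assume 20% of controls ordered, 60-80% ordered under intervention, the same odds gap in both periods and no true effect. The same algebra in each period gives 2.1 to 9.5 points of false harm if lower-risk patients are ordered, and 2.2 to 10.5 points of false benefit if higher-risk patients are. Restricting both sides does not remove the bias when the ordered share differs between periods.

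These are contrasts of rates. They are not operating characteristics of the planned GEE model.

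**The case against.** The analysis is labelled additional, the primary analysis is ITT, and no decision rule in the documents depends on the per-protocol result. Section 5.2.4 even says all comparisons of treatment and control use ITT. For utilization, the weakness is one that almost any per-protocol analysis shares. This stands, and it is why the point is minor.

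The design also pushes toward high uptake. PowerPlan initiation is a care gap monitored daily (section 7.1.4), and coordinators alert staff to close gaps (synopsis). In the Appendix A workflow the coordinator pages a provider who has not used the PowerPlan and proposes starting the pathway. A share of 90% or more is as defensible an assumption as 60-80%, and with all controls as comparator the utilization bias is then small. This stands too.

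The overlap between selection and outcome is not total. Appendix A, which is marked as a pilot version, foresees "PP RT orders modified/deselected" and has the coordinator "Verify steroid/antibiotic ordered and administered". This limits the order-rate problem without removing it.

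A reader might go further and infer three things that the documents do not support.

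- *The ordered-only analysis will favor the pathway.* Nothing in the documents shows whether lower- or higher-risk patients are ordered, so the direction is open.
- *A true 10-point effect would be understated by a known amount.* Ten points is the planned overall effect. The effect in ordered patients could be larger: if patients not ordered gained nothing, it would be 10/0.6 = 16.7 points at 60% ordered. No firm benchmark exists.
- *Every patient left out was treated.* Section 4.4.1 says patients are subject to receiving components, not that they received them.

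**Conclusion.** The concern holds in two parts of unequal strength.

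The order-rate part follows from the text and needs no assumption about patient risk. As written, the per-protocol plan covers outcomes that its own selection criterion largely contains. The illustrative false gain of 5 to 20 points rests on assumed order rates and shrinks as uptake nears 100%. Three of eight secondary outcomes are involved if the ordering event is the PowerPlan, mainly one if it is the respiratory protocol.

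The utilization part is right in principle, but its size is unknown. With all control patients as comparator and an assumed odds gap of 1.25 to 2.0, the bias is 1.1 to 6.8 points in either direction at 60-80% ordered and 0.3 to 1.7 points at 90-95%, against a design effect of 10 points. The reassurance from high uptake applies only to that comparator.

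It would be wrong to infer that the trial's main result is compromised: the ITT primary analysis does not use the ordered-only denominator. This is a cheap improvement of minor severity.

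**What to change.** Rewrite the per-protocol sentence in section 5.2.5 as follows.

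1. Report the antibiotic, steroid and short-acting bronchodilator order rates by ITT only, and exclude them from the ordered-only analysis.
2. Run the actual-intervention-period analysis on its own. Keep all J44.1 patients, classify them by each hospital's actual go-live date, and use the primary model.
3. If an ordered-only utilization contrast is kept, name the ordering event (PowerPlan or respiratory protocol), state the control denominator, adjust for baseline covariates, and label the result non-randomized and exploratory.

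Dropping the formal ordered-only utilization test altogether is a further option on which statisticians could differ; the problem does not require it.

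The cost is one rewritten sentence. Use of the PowerPlan and of the respiratory protocol is already tracked for the monthly summary (section 5.6), and the go-live analysis reuses the planned model. Sites, sample size and the primary analysis do not change. The downsides are that the three order rates lose a per-protocol result, and that the go-live analysis is not protected by randomization if a hospital's delay is related to its outcomes.

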5.2.6 Missing data

All the related available electronic data will be pulled without missing any subjects. Thus, the missing of outcome variables are less likely to occur. However, the missing information on covariables is unavoidable. Sensitivity analyses are recommended for trials with missing data. We will compare baseline characteristics such as age, gender, and health insurance status between patients with complete follow-up data to those with missing data by intervention period to assess potential biases that may exist in the complete case analysis. We will conduct sensitivity analyses for the primary and secondary outcomes using several methods which have different missing data assumptions: (1) complete case analyses which assumes missing completely at random; (2) multiple imputation using $M=10$ imputations, which assumes missing at random; and (3) assigning poor scores and good scores for missing values differentially by treatment group, which aligns with non-ignorable missingness (the data missingness is related to the actual value).

5.3 Training

Beginning two to three weeks prior to first patient enrolment at the respective facility, the COPD pathway coordinator and those responsible for discharge will begin training on the materials supporting the pathway as well as use of the pathway itself. This will include communication touchpoints between the coordinator, discharge facilitator as well as the individuals responsible for the clinical path. Specifically, there will be education on the COPD protocol, Education Checklist, the COPD clinical pathway and order set as well as the criteria and fulfillment options required for discharge.

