4.3 Participating Sites

As part of the research design and rollout of this project, randomization will occur at the site level. CORE has randomized the facility participation order in advance of project kickoff. Site enrollment will begin with two facilities, adding on 2 additional facilities on a rolling basis in 2 month intervals, until all 8 facilities are active in using the COPD pathway. Once added, sites will begin utilizing the COPD clinical pathway in their daily practice with the target patient population.

The following Carolinas Healthcare System sites will be randomized for participation in this project.

- Carolinas HealthCare System Cleveland
- Carolinas HealthCare System Kings Mountain
- Carolinas HealthCare System Lincoln
- Carolinas HealthCare System NorthEast
- Carolinas HealthCare System Pineville
- Carolinas HealthCare System Union
- Carolinas HealthCare System University
- Carolinas Medical Center

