5.2.2 Randomization and allocation

The stepped wedge design implies a baseline period, in which no clusters are exposed to the intervention¹². Then, at the chosen time interval of two months, two hospitals will be randomized to cross from the control to intervention (**Figure 1**). This process continues until all eight hospitals have crossed over to the intervention. The order of this cross over process will be randomized. We will use block randomization to assign two hospitals at a time to switch from the control to intervention using SAS Enterprise Guide version 6.1. Allocation will be communicated only to hospital senior leadership initially to prevent contamination. Others including providers at the hospital will learn of allocation in the month preceding roll-out. Patients in included hospitals will be blinded to the intervention or control period.

[figure not shown]
Figure 1. The stepped wedge study design

| | 1-Apr | 1-Jun | 1-Aug | 1-Oct | 1-Dec | |
|-----------|-------|-------|-------|-------|-------|-----------------------------|
| Cluster 1 | 0 | 1 | 1 | 1 | 1 | 0=control 1=intervention |
| Cluster 2 | 0 | 1 | 1 | 1 | 1 | |
| Cluster 3 | 0 | 0 | 1 | 1 | 1 | |
| Cluster 4 | 0 | 0 | 1 | 1 | 1 | |
| Cluster 5 | 0 | 0 | 0 | 1 | 1 | |
| Cluster 6 | 0 | 0 | 0 | 1 | 1 | |
| Cluster 7 | 0 | 0 | 0 | 0 | 1 | |
| Cluster 8 | 0 | 0 | 0 | 0 | 1 | |

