5.2.3 Sample size analysis

Calculations of sample size were based on the primary endpoints of 60-day non-elective acute care utilization. With the assumption of detecting a change in rates of 60-day non-elective acute care utilization from 43% in the control period to 33% in the intervention period, 59 patients with COPD exacerbation per hospital per two months is needed to achieve a power of 0.80 (intra-class correlation coefficients (ICC)=0.05 and two-side $\alpha=0.05$. Holding other parameters constant, the larger ICC is, the higher the power we will obtain (**Figure 2**). With sample sizes per cluster per two months ranging from 30 to 158, our preliminary data shows that the coefficient of variation (CV) of sample size is approximately 0.5. To account for this varying cluster size, we inflated the number of patients by 25% resulting in an average of 74 patients per hospital per two months¹³, resulting in a total sample size of 2960 patients among the intervention group and 5920 patients overall inclusive of our control population. The power was calculated by using the PASS 15¹⁴.

Figure 2. Alternative Sample Size Estimation

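### Do the staff-training weeks before each hospital's crossover contaminate the control data enough to need an analysis of their own?

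*Combined protocol and SAP*

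**What the plan says.** Section 5.3 fixes the training lead time: "two to three weeks prior to first patient enrolment at the respective facility, the COPD pathway coordinator and those responsible for discharge will begin training". The content includes "the COPD clinical pathway and order set as well as the criteria and fulfillment options required for discharge". Section 5.2.2 staggers disclosure. First, "Allocation will be communicated only to hospital senior leadership initially to prevent contamination"; then "Others including providers at the hospital will learn of allocation in the month preceding roll-out".

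Figure 1 in that section has eight hospitals, five two-month periods and only 0 or 1 in each cell. Section 4.3 ties the start of pathway care to the site being added: "Once added, sites will begin utilizing the COPD clinical pathway in their daily practice with the target patient population".

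Section 5.2.5 makes the primary analysis intention-to-treat. It adds a per-protocol analysis based on "those who had pathway ordered as well as intervention periods when truly occurred", within-cluster comparisons, and "comparisons of a series of (unbalanced) quasi-parallel cluster trials between those enrolled and unenrolled clusters at each intervention enrollment period". Section 5.6 lists order-set (PowerPlan) and bronchodilator-protocol use in a monthly summary, and Section 4.1 runs the patient list at all eight hospitals throughout.

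**The concern.** Staff who have just been taught an order set and a discharge checklist may start using them. Any such use before crossover sits in cells coded 0, makes the control outcome look more like the intervention outcome, and pulls the estimate toward no effect.

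The timing makes this more than trivial. The exposed days are the last of each hospital's control time, and a stepped-wedge estimate leans heavily on those cells. The quasi-parallel comparisons do not escape either: in the June, August and October periods, 2 of 6, 2 of 4 and 2 of 2 control hospitals are about to cross over. If the trial then showed a smaller effect than planned, a reader could not tell a weak pathway from a diluted control.

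**Working it through.** **Inputs.** From Section 5.2.3: 43% versus 33%, ICC 0.05, two-sided alpha 0.05, 59 per hospital per two months for 80% power, 74 after inflation. From Figure 1: 8 hospitals, 5 periods, 2 hospitals per step, and 61 days in each period from 1 April to 1 December. From Section 5.3: 14 to 21 days. Assumed: first patient enrolment means go-live, admissions are even over time, and cells are equal in size. Early-uptake shares are assumptions; the documents give none.

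**The plan's own figure.** Generalised least squares with fixed period effects, a random hospital intercept, a common effect and variance 0.43 × 0.57 gives SE 0.0356 at 59 per cell. Power = Φ(0.10/0.0356 − 1.96) = 0.80, as stated. At 74 per cell the SE is 0.0319 and power 0.88.

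**Exposed time.** 14/61 = 23% to 21/61 = 34% of each last control period. Over all control time: 8 × 14 = 112 to 8 × 21 = 168 of 20 × 61 = 1,220 hospital-days, or 9.2% to 13.8%. At 74 per cell, 8 × 74 × 21/61 = 204 admissions at most.

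**Dilution.** The net weight of the eight last-control cells is −0.968 at 74 per cell. Expected reading = 10 × (1 − 0.968 × d/61 × share):

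| Assumed share of effect already present | 14 days | 21 days | Power at 74 per cell |
|---|---|---|---|
| 0% | 10.0 | 10.0 | 0.88 |
| 10% | 9.8 | 9.7 | 0.87–0.86 |
| 25% | 9.4 | 9.2 | 0.84–0.82 |
| 50% | 8.9 | 8.3 | 0.80–0.74 |
| 100% | 7.8 | 6.7 | 0.68–0.55 |

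**Model dependence.** Section 5.2.5 plans GEE. With an independence working correlation and period effects the weight is −0.60, so 50% over 21 days reads 10 × (1 − 0.60 × 0.344 × 0.5) = 9.0 rather than 8.3. With period-specific effects, closer to the planned interaction, the weight runs from −0.66 (June) to −1.42 (October), giving 8.9 to 7.6 in the same scenario.

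**What excluding the weeks would buy.** Dropping the last 21 control days raises the SE at 74 per cell from 0.0319 to 0.0344 and lowers power from 0.88 to 0.83. It gains power only if 1 − 0.968 × 0.344 × share falls below 0.0319/0.0344, that is, at a share above about 22%. The difference between the two estimates has SE √(0.0344² − 0.0319²) = 0.0129. Shifts of 0.56 points (14 days, 25%) to 1.67 points (21 days, 50%) give z of 0.43 to 1.29, which would be detected about 7% to 25% of the time.

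**What a table of order-set use would buy.** Pooled over hospitals, 204 admissions against 20 × 74 − 8 × 74 × 30/61 = 1,189 earlier control admissions give a 95% half-width of 1.96 × √[p(1 − p)(1/204 + 1/1,189)]. That is 5.9 points at an assumed 20% use and 7.4 at 50%, taking admissions as independent. One average hospital has 74 × 21/61 = 25 admissions in the window, against about 38 earlier ones at the first two sites and 260 at the last two; the half-width is then about 16 to 25 points.

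**The case for a change.** The strongest case for a change is that the protocol itself treats contamination as a risk, since it restricts early disclosure, yet nothing checks whether the restriction worked. The per-protocol analysis is loosely worded: it sets no rule for a hospital's true start, nor for a control-period patient who had the pathway ordered. The monthly summary does not say that it covers control hospitals or separates the weeks before crossover. The order data are already held, and a table chosen in advance is more credible than one produced after a disappointing result.

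Much of this stands as description. No analysis is defined for these weeks, the dilution would run toward the null, and under period-specific effects it could exceed the common-effect figures. What does not follow is that the plan is wrong. Every non-zero uptake share is supposed rather than documented. The people named for training are the coordinator and discharge staff, while the synopsis says the care steps are driven mainly by providers using the order set. The per-protocol clause, although thin, is directed at actual delivery and gives analysts a place to handle early use.

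**Conclusion.** The observation is accurate but calls for no change. Keeping the randomised crossover dates in an intention-to-treat primary analysis without a transition window is a fair trade-off: removing up to 204 of 2,960 admissions (74 × 40 cells) costs about 5 power points for certain, to guard against early use that the documents do not report.

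If there was none, the bias is zero. At an assumed 25% the common-effect reading is 9.4 to 9.2 points. At 50% over 21 days it is 8.3 points under the random-intercept model and 9.0 under independence. These figures are illustrative: risk-difference scale, equal cells, no logit link. They use 74 per cell, although Section 5.2.3 reports "a total sample size of 2960 patients among the intervention group and 5920 patients overall inclusive of our control population". If 5,920 filled the same 40 cells (148 each), power at 50% over 21 days would still be about 0.95.

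An added exclusion analysis could neither establish nor rule out dilution, and a hospital-level table would be too imprecise to settle it. Analysts can say in the per-protocol report how control-period patients with the pathway ordered were handled, and can show order-set use before crossover pooled over the eight hospitals. Both are sensible reporting choices that leave the primary analysis as it is.
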